7.3 Pharmacodynamic Analyses

Urinary glucose excretion (UGE) and creatinine normalized UGE (nUGE) will be determined as PD parameters at baseline and up to 48 hours post-dose.

UGE_{t1-t2} (g) will be derived from urine volume and glucose concentration as follows:

[urine volume (V_{t1-t2} , mL) x glucose concentration (mg/dL)/100]/1000.

UGE normalized by urinary creatinine will be calculated as per below:

[urine volume (V_{t1-t2} , mL) x creatinine concentration (mg/dL)/100]/1000.

The total 24-hour and 48-hour quantity of glucose excreted in urine will be calculated by adding the amounts collected during each post-dose interval.

Descriptive statistics will be used to describe any differences in these PD parameters between treatment groups (normal hepatic function and moderate hepatic impairment).

For PD data, reported pre-dose values that are below the defined limit will be set to zero. Any missing values or values below the reported defined limit that appear after pre-dose for PD data (glucose, UGE, creatinine) will be set to missing. Because zero values cannot be included in calculation of a geometric mean, then geometric means and percent CV calculated for data including values below the defined limit will be based only on the subjects without such zero value data

PD data will also be reported in listings.

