9.6 Pharmacodynamic Analysis

The PD parameters, glucose concentrations, creatinine concentrations, UGE and UGE normalized by urinary creatinine, including UGE_{t1-t2} over specified time interval, and total 24-hour, 48-hour UGE, will be determined. UGE_{t1-t2} (mg) will be derived from urine volume (V_{t1-t2} , mL) \times glucose concentration ($mg\ dL^{-1}$) / 100. UGE and nUGE will be listed and summarized by hepatic function group using descriptive statistics.

Reported predose values for PD data that are below the defined limit will be set to zero. Any missing values or values below the reported defined limit that appear after predose for PD data will be set to missing.

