AUC_{0-t}	area under the plasma concentration-time curve from the time of dosing (Time 0) to Time t
$AUC_{u(0-t)}$	area under the unbound plasma concentration-time curve from time 0 to time t
BLOQ	below the limit of quantitation
BMI	body mass index
BUN	blood urea nitrogen
Ca	calcium
CI	confidence interval
Cl	chloride
C_{last}	concentration corresponding to T_{last}
CL/F	apparent oral clearance
CL_u/F	apparent clearance relative to unbound drug concentration
cm	centimeter

GLOSSARY OF ABBREVIATIONS

C_{max}	maximum observed plasma concentration
C_{maxu}	maximum unbound plasma concentration
cps	cycles per second
CRF	case report form
CV	coefficient of variation
DBP	diastolic blood pressure
dL	deciliter
DM	data management
ECG	electrocardiogram
f_u	Unbound fraction, calculated as (free drug concentration)/(total drug concentration)
hr	hour(s)
HbsAg	hepatitis B surface antigen
Hct	hematocrit
HCV	hepatitis C virus
HDL-C	high density lipoprotein cholesterol
Hgb	hemoglobin
HIV	human immunodeficiency virus
ICF	informed consent form
INR	international normalized ration
IRAE	immediately reportable adverse event
K	potassium
kg	kilogram
KR	Kenward-Roger
L	liter
λ_z	terminal elimination phase rate constant

GLOSSARY OF ABBREVIATIONS

LC-MS/MS	liquid chromatography/mass spectrometry
LDL-C	low density lipoprotein cholesterol
LLN	lower limit of normal
LS	least square
max	maximum
MCH	mean corpuscular hemoglobin
MCHC	mean corpuscular hemoglobin concentration
MCV	mean corpuscular volume
MDMA	methylenedioxymethamphetamine
MedDRA	Medical Dictionary for Regulatory Activities
mg	milligram
min	minute
mL	milliliter
msec	millisecond
Na	sodium
NCA	non compartmental analysis
NTR	not treatment related, includes unrelated
nUGE	creatinine normalized UGE
OTC	over the counter
PCP	phencyclidine
PCS	potentially clinically significant
PD	pharmacodynamic
PE	physical examination
PK	pharmacokinetic
PR	The period that extends from the beginning of the P wave (the onset of atrial depolarization) until the beginning of the QRS complex (the onset of ventricular depolarization).

GLOSSARY OF ABBREVIATIONS

PT	preferred term
QA	quality assurance
QC	quality control
QRS	The combination of three of the graphical deflections seen on a typical electrocardiogram.
QT	Time from electrocardiogram Q wave to the end of the T wave corresponding to the electrical system
QTcB	QT corrected using Bazetts formula [$QT/(RR^{1/2})$]
RBC	red blood cell (count)
REML	restricted maximum likelihood

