The ratios of geometric least squares means and corresponding 90% confidence interval (CI) for the treatment comparison will be determined by exponentiating the mean differences between treatments on the logarithm scale.

The appropriateness of the mixed model will be assessed through residual analyses. Any modifications required due to poor fit will be reported and executed.

Refer to Appendix 2 for the SAS code.

Descriptive statistics of total and unbound plasma concentration time data will be summarized by hepatic function group and timepoint.

A listing of bexagliflozin concentration-time data by Subject Number, hepatic function group and timepoint will be provided.

The PK parameters C_{max} , t_{max} , λ_z , $t_{1/2}$, CL/F, V_z/F , AUC_{0-t} , AUC_{0-24} , $AUC_{0-\infty}$, AUC_{extr} , $AUC_u(0-t)$, $AUC_u(0-\infty)$, $C_{max,u}$, and Cl_u/F will be summarized by hepatic function group for bexagliflozin.

Descriptive statistics of total and unbound PK parameters will be summarized by hepatic function group for the PK Population.

Means, standard deviation (SD), medians, ranges (min, max) and geometric means and coefficients of variation will be presented for all parameters with the exception of T_{max} . Medians and ranges will be presented for T_{max} .

A listing of derived PK parameters of bexagliflozin for total and unbound bexagliflozin by Subject Number and hepatic function group will be provided.

Descriptive statistics for urinary glucose concentrations, urinary glucose excretion (UGE), urinary creatinine concentrations, and urinary glucose/creatinine by hepatic function group and collection interval will be summarized for the PD Population. Because concentration values that were below the limit of quantitation (BLOQ) prior to T_{max} will be set to zero, which cannot be included in calculation of a geometric mean, then geometric means and percent CV calculated for data including BLOQ values will be based only on the subjects with non-BLOQ data

A listing of urinary PD parameters will be provided by Subject Number, hepatic function group and collection interval.

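### The SAP formula for creatinine-normalised urinary glucose has no glucose term: it returns grams of creatinine excreted

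*SAP*

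**What the plan says.** SAP 7.3 sets out the pharmacodynamic parameters: "Urinary glucose excretion (UGE) and creatinine normalized UGE (nUGE) will be determined as PD parameters at baseline and up to 48 hours post-dose". It derives UGE in grams as "urine volume (V_{t1-t2} , mL) x glucose concentration (mg/dL)/100]/1000". It then announces "UGE normalized by urinary creatinine will be calculated as per below" and prints "urine volume (V_{t1-t2} , mL) x creatinine concentration (mg/dL)/100]/1000".

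The other descriptions of this parameter point to a glucose quantity scaled by creatinine:

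- The SAP glossary expands nUGE as "creatinine normalized UGE".
- SAP 7.2 plans descriptive statistics for "urinary creatinine concentrations, and urinary glucose/creatinine by hepatic function group and collection interval will be summarized for the PD Population".
- Protocol 9.6 lists "UGE and UGE normalized by urinary creatinine", but gives a formula for UGE only.
- The Protocol synopsis also lists urinary glucose normalised by creatinine, without a formula.

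PD is part of the primary objective (Protocol 2.1, SAP 2.1). Protocol Section 1 identifies glucosuria as the drug's main pharmacodynamic effect.

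**The concern.** The expression printed for nUGE is the UGE expression with creatinine substituted for glucose. It has no glucose numerator and no division by creatinine. Because it is the only explicit derivation of nUGE in either document, it is the one a programmer following the SAP would code.

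The nUGE table would then compare creatinine output between the hepatic groups under a label that promises a comparison of glucosuria. Nothing in the planned analysis would force the error into view. The pharmacodynamic results are descriptive, with about eight subjects per group, so the summary table is the result.

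**Working it through.** **Inputs.** For each collection interval, Protocol 6.6.2.3 provides the urine volume V (mL), the glucose concentration G and the creatinine concentration C. Both concentrations are in mg/dL in the SAP formulas. The documents give no expected values, so every number below is an illustrative assumption.

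**Step 1: units.** There are 100 mL in a dL, so V × concentration / 100 is in mg, and a further division by 1000 gives g.

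- UGE as printed: V × G / 100 / 1000 = g of glucose. This agrees with Protocol 9.6, which stops at mg (V × G / 100).
- nUGE as printed: V × C / 100 / 1000 = g of creatinine.

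**Step 2: the intended quantity.** Dividing the first by the second, volume and scale factors cancel: (V × G / 100 / 1000) / (V × C / 100 / 1000) = G / C, in g/g.

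**Step 3: one collection.** Assume V = 1500 mL, G = 1500 mg/dL, C = 60 mg/dL.

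- UGE = 1500 × 1500 / 100 / 1000 = 22.5 g
- Printed nUGE = 1500 × 60 / 100 / 1000 = 0.9 g creatinine
- Intended nUGE = 22.5 / 0.9 = 25 g/g, which equals 1500 / 60

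Setting G to 0 leaves the printed result at 0.9.

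**Step 4: range.** Assume creatinine excretion of 0.4, 0.7 or 0.9 g per 12 h, and UGE from 0.05 g to 25 g, a 500-fold range.

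| Creatinine (g/12 h) | Printed nUGE, any UGE | Intended, UGE 0.05 g | Intended, UGE 10 g | Intended, UGE 25 g |
|---|---|---|---|---|
| 0.4 | 0.4 | 0.125 | 25.0 | 62.5 |
| 0.7 | 0.7 | 0.071 | 14.3 | 35.7 |
| 0.9 | 0.9 | 0.056 | 11.1 | 27.8 |

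The printed formula does not move across a row; it only returns the creatinine mass.

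**Step 5: group comparison.** Assume equal UGE of 20 g in both groups, with creatinine of 0.5 g (impaired) and 0.7 g (control).

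- Printed formula, impaired/control: 0.5 / 0.7 = 0.71
- Intended ratio, impaired/control: (20 / 0.5) / (20 / 0.7) = 40 / 28.6 = 1.40

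With equal UGE the two answers are reciprocals, so they point in opposite directions.

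**Step 6: incomplete collections.** Within an interval G / C does not depend on V. The printed expression is proportional to V, so at given concentrations any urine lost from a collection lowers it directly.

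**The case against.** The best counter-argument is that the intent is plain. SAP 7.2 calls the quantity urinary glucose/creatinine, and the glossary and the Protocol agree. A careful programmer would probably divide the two amounts. The table shells are in a separate document and may name the right variable and unit. Glucose and creatinine concentrations and UGE are also to be summarised, with a by-subject listing, so a creatinine-only column could be noticed and the ratio recomputed. SAP 3.3 plans no hypothesis testing, and no confidence interval, boundary or sample size depends on nUGE. UGE and its 24 h and 48 h totals measure glucosuria directly and are correctly defined.

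Most of this stands as a limit on the consequence. It is not certain that a creatinine table would be published as nUGE, and no data would be lost if it were. None of it makes the formula right. A programmer who corrected it silently would depart from the written plan, although SAP Section 4 says that endpoints and analytic approaches are defined prospectively.

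One point of wording also stands. Protocol Section 1 reports slight rises in creatinine with the drug, so an incidental drug effect on creatinine excretion cannot be excluded. The exact statement is that the printed quantity carries no glucosuric effect.

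A numerator dropped from the printed line is conceivable but unlikely: the brackets balance, and the parallel UGE line just above is intact.

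**Conclusion.** The formula is wrong as written. It gives the mass of creatinine excreted, in grams, and is unaffected by urinary glucose. That conclusion follows from the units alone and needs no assumed values. The sizes shown (0.9 against 25 g/g in one collection; group ratios of 0.71 against 1.40) rest on assumed volumes, glucose and creatinine outputs, and serve only to show that the discrepancy can be large and can reverse a comparison.

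The damage is confined to nUGE, a named pharmacodynamic parameter under the primary objective. UGE, the pharmacokinetic analysis and the sample size are unaffected. Because this is an explicit derivation that measures the wrong analyte, it should be corrected before database lock.

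**What to change.** In SAP 7.3, replace the nUGE expression with:

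nUGE(t1–t2) = UGE(t1–t2) in g / creatinine excreted over t1–t2 in g, reported in g/g.

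The creatinine expression now printed can stay, relabelled as the denominator. It would help to add that, within one pooled collection, nUGE equals the glucose concentration divided by the creatinine concentration.

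If nUGE is also to be reported over 0–24 h and 0–48 h, say how it is formed; summed glucose over summed creatinine is a natural choice. The documents specify cumulative totals for glucose but do not clearly call for a cumulative nUGE, so this is a clarification.

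The table shells should be checked for the same definition and unit. The cost is a line or two of text and one derivation. Volume, glucose and creatinine are already recorded for every batch, and SAP Section 10 provides for a revision before database lock.

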2 STUDY OBJECTIVES

2.1 Primary Objective

To evaluate the effect of moderate hepatic impairment on the pharmacokinetics (PK) and pharmacodynamics (PD) of a single oral dose of bexagliflozin tablets, 20 mg

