9.2 Determination of Sample Size

The sample size for this study is not based upon formal statistical consideration. The sample size is considered adequate to detect clinically relevant PK or PD differences between healthy and hepatic impairment subjects.

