3.3 Hypothesis Testing

No formal statistical hypothesis testing will be conducted for this study.

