3.5 Sample Size

The sample size for this study is not based upon formal statistical consideration. The sample size is considered adequate to detect clinically relevant PK differences between healthy and hepatic impairment subjects.

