5.3 Pharmacodynamic Population

The PD Population will include all subjects without major protocol violations who have been dispensed study drug and who have received study drug and who have had pre-dose urine collection and at least a postdose 0-12 hr urine sample collected. The PD Population will be used to summarize the PD parameters.

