AUC_{0-24} , AUC_{0-t} , and $AUC_{0-\infty}$ will be calculated using the linear trapezoidal linear interpolation method, using actual elapsed time values. If the actual collection time is unknown the nominal collection time may be used for the purposes of PK parameter estimation. For the purpose of calculating AUC, all missing values will be treated as missing in the PK analysis and excluded from analysis except when they occur at pre-dose where they will be set to zero. All values that were below the limit of quantitation (BLOQ) prior to T_{max} will be set to zero. BLOQ values that occur after T_{max} will be set to missing. When ≥ 2 consecutive plasma concentrations that are BLOQ are encountered after T_{max} , these and all subsequent values will be excluded from the analysis.

$AUC_{0-\infty}$ will be calculated as outlined below:

$AUC_{0-\infty} = AUC_{last} + (C_{last} / \lambda_z)$, where C_{last} is the last temporal quantifiable plasma concentration corresponding to T_{last} .

The proportion of $AUC_{0-\infty}$ due to extrapolation (AUC_{extr}) will be calculated and expressed as a percentage. $AUC_{0-\infty}$ values will be considered unreliable estimates if the AUC_{extr} is greater than 20% and will be excluded from summary tables but will be listed.

CL/F will be calculated as $Dose/AUC_{0-\infty}$.

V_z/F will be calculated as $Dose/(\lambda_z \times AUC_{0-\infty})$.

$T_{1/2}$ will be calculated as $0.693/\lambda_z$.

The fraction unbound (f_u) will be calculated as free drug concentration/total drug concentration.

The apparent clearance relative to the unbound drug concentration (Cl_u/F) will be calculated as $Cl_u/F = Dose/AUC_u$.

Listings of plasma concentrations by Subject Number, hepatic function group, and timepoint will also be provided.

To assess the effect of moderate hepatic impairment on the PK of bexagliflozin, an analyses of variance (ANOVA) with a fixed effect corresponding to the hepatic function group (normal or moderate hepatic impairment) will be fitted to the natural logarithmic transformation of PK parameters (C_{max} , AUC_{0-t} and $AUC_{0-\infty}$). The 90% confidence intervals will be constructed for the ratio of least squares (LS) geometric means of PK parameters (total and unbound C_{max} , AUC_{0-t} and $AUC_{0-\infty}$) for the moderate hepatic function group vs the normal group, with 80-125% defined as the boundaries for subjects in the PK Population.

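### PD shares the primary objective with PK but gets only group summaries; a planned UGE ratio with 90% CI, unadjusted and adjusted, would be a cheap improvement

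*SAP*

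**What the plan says.** Protocol 2.1 sets one primary objective: "To evaluate the effect of moderate hepatic impairment on the pharmacokinetics (PK) and pharmacodynamics (PD) of a single oral dose". SAP 2.1 repeats it.

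For PK, SAP 7.2 fits a log-scale model with hepatic function group as the fixed effect and states: "The 90% confidence intervals will be constructed for the ratio of least squares (LS) geometric means of PK parameters". For PD, SAP 7.3 states: "Descriptive statistics will be used to describe any differences in these PD parameters between treatment groups". Protocol 9.6 agrees: "UGE and nUGE will be listed and summarized by hepatic function group using descriptive statistics". Geometric means and CVs by group are foreseen for PD, but no between-group ratio or interval.

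SAP 3.3 states: "No formal statistical hypothesis testing will be conducted for this study". The PK intervals are planned under that same clause.

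The PD Population (SAP 5.3) takes subjects "who have had pre-dose urine collection and at least a postdose 0-12 hr urine sample collected". SAP 7.3 builds the 24 h and 48 h totals by summing the postdose intervals, and sets postdose values that are missing or below the limit to missing. It does not say what happens to a total that lacks an interval.

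**The concern.** Two halves of one objective are reported differently. For PK the reader sees an estimate of the group effect and how precise it is. For PD the reader sees two columns of summary statistics and must judge the difference by eye.

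This matters most if the groups look alike. With about eight subjects each, similar UGE summaries could be compatible with a sizeable loss or gain of effect, and nothing in the planned output would say how large a difference remains possible.

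The comparison is also not a clean one. Protocol 1 says that glucosuria rises with GFR and plasma glucose, and Protocol 4.1 matches controls on age, weight, sex and smoking only. Diabetes is not an exclusion. Exclusion 25 bars recent prescription drug use in controls, while exclusion 23 bars only new prescriptions in the hepatic group, so treated diabetes can in effect enter the hepatic group alone. A bare ratio would carry these differences without showing them, as the descriptive summaries would too.

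**Working it through.** **1. The plan's own figures.** Inputs: dose 20 mg; ED50 of 3.6 mg (healthy) and 1.2 mg (diabetic), from Protocol 1.2. Share of maximal UGE = dose / (dose + ED50).
- Healthy: 20 / 23.6 = 84.7%.
- Diabetic: 20 / 21.2 = 94.3%.

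These agree with the 85% and 94% in Protocol 1.2 and 3.2.2. The sample size of about 16 cannot be reproduced: Protocol 9.2 and SAP 3.5 give no effect size, variance or power.

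**2. Room for an exposure-driven rise.** Under the same model, at fixed glucose and GFR, the largest possible rise is 23.6 / 20 = 1.18-fold (healthy) or 21.2 / 20 = 1.06-fold (diabetic). Similar UGE in the two groups is thus expected even if exposure rises several-fold. The documents do not state the collection interval behind the 85% and 94%. I take them as applying to UGE 0-24 h, by assumption; nothing comparable can be derived for 0-48 h.

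**3. Precision of a UGE ratio.** Log-scale SD: s = sqrt(ln(1 + CV²)). Half-width: h = t(0.95, n1 + n2 − 2) × s × sqrt(1/n1 + 1/n2). The interval is the ratio multiplied and divided by exp(h). Example, 8+8 at CV 30%: s = sqrt(ln 1.09) = 0.294; h = 1.7613 × 0.294 × 0.5 = 0.259; factor 1.30. The CVs are assumptions.

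| Subjects | t | CV 20% | CV 30% | CV 40% | CV 50% |
|---|---|---|---|---|---|
| 8+8 | 1.7613 | 1.19 | 1.30 | 1.40 | 1.52 |
| 7+7 | 1.7823 | 1.21 | 1.32 | 1.44 | 1.57 |
| 6+6 | 1.8125 | 1.23 | 1.36 | 1.50 | 1.64 |

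Around an observed ratio of 1.00 with 8+8, the lower limits are 0.84, 0.77, 0.71 and 0.66. At CV 30%, for example, the data would be compatible with anything from 23% less to 30% more UGE.

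For an observed ratio at the step 2 ceiling to exclude 1 with 8+8, s must be below ln(1.18) / (1.7613 × 0.5) = 0.188 (CV 19%) or ln(1.06) / (1.7613 × 0.5) = 0.066 (CV 6.6%).

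**4. What confounding could do.** A simulation with no hepatic effect, 8+8 and 4,000 runs took UGE as proportional to GFR × glucose. Assumed control means were GFR 100 and glucose 95 mg/dL. Assumed log SDs were 0.15 for GFR, 0.07 (controls) and 0.25 (hepatic group) for glucose, and 0.25 residual.

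| Hepatic group mean | Unadjusted ratio | Coverage of nominal 90% CI |
|---|---|---|
| GFR 85 | 0.85 | 76% |
| GFR 75 | 0.75 | 53% |
| Glucose 125 | 1.32 | 55% |
| Glucose 150 | 1.58 | 18% |
| GFR 75 and glucose 125 | 0.99 | 90% (the biases cancel) |

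Adjusted for log GFR and log glucose, the ratio was 1.00 with coverage of 89-91%. That recovery follows largely from the assumed form; the documents give only the direction of the dependence. Moving from 14 to 12 degrees of freedom changes the CV 30% factor only from 1.295 to 1.299, but imbalance in the covariates would widen the interval further.

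**5. The totals.** A subject with only the 0-12 h collection is in the PD Population. Read one way, the 24 h total is then missing; read another, it is a partial sum that understates UGE. A collected interval with glucose below the limit falls into the same gap. Dropping that subject would select on the outcome, possibly more often in one group.

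**The case against.** The strongest case against is that the protocol and SAP agree on descriptive PD, that no hypothesis is tested, and that a reader can approximate a ratio and interval from the planned geometric means and CVs. All of that is true, and it is why this is an improvement only. It does not argue against planning the estimate: SAP 3.3 already coexists with PK intervals, and a planned figure is checked and has a defined set of subjects behind it.

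The second objection is that an unadjusted ratio mixes the hepatic effect with glucose and GFR. This stands, and is why the ratio should not appear alone. But the descriptive comparison has the same confounding and shows no uncertainty. Nor does adjustment simply replace the unadjusted ratio: if impairment itself alters glucose or GFR, the adjusted estimate answers a different question. With 16 subjects, and diabetes possibly in one group only, it may also rest on extrapolation.

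Third, much of the context is already planned. SAP 6.1 and 8.3 summarise laboratory values and medical history by group, and SAP 7.2 and 7.3 cover predose UGE. Only derived eGFR and placement beside the PD result are new.

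A reader might also infer that descriptive-only PD contradicts a claim that the trial was sized for PD, since Protocol 9.2 mentions PK or PD differences and SAP 3.5 mentions PK only. Neither statement has a calculation behind it, and the point does not rest on them.

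**Conclusion.** The point holds as a modest improvement. No planned output gives the PD group difference with its uncertainty, although PD is half of the primary objective and PK has exactly such an output. At 8+8 the 90% factor would be 1.19 to 1.52 for assumed CVs of 20 to 50%.

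Three stronger readings are tempting, and the documents do not support them:

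- **That the descriptive plan is an error.** It is a permissible phase 1 choice, stated consistently in both documents.
- **That controls and patients will differ in glucose or GFR.** The design allows it and does not match on either, but that is not evidence of imbalance in this trial. The simulated biases depend on assumed imbalances and an assumed proportional form.
- **That a ratio above 1.18 or 1.06 shows something other than exposure.** That ceiling assumes fixed glucose and GFR, and that the 85% and 94% figures describe UGE 0-24 h. It must not be applied to 0-48 h, where a longer effect could add glucose.

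**What to change.** Before database lock, add to SAP 7.3, as estimation only and without acceptance limits:

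1. The geometric mean ratio (moderate impairment versus normal) with 90% CI for UGE 0-24 h and UGE 0-48 h in the PD Population, from a log-scale model with hepatic function group as the fixed effect, labelled unadjusted.
2. Beside it, a prespecified supportive estimate adjusted for log baseline eGFR and log predose plasma glucose, using the SAP 8.4 baseline (last evaluation before dosing).
3. In the same table, by group: eGFR, predose glucose, predose UGE and diabetes history.
4. A rule for totals. A 24 h or 48 h total is missing only if a contributing interval was not collected. A collected interval with below-limit glucose counts as zero, with a sensitivity analysis at the limit. This replaces setting it to missing. Report by group how many subjects each part of the rule affects.

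Item 4 is worth adopting even if the ratio is not, because the totals are already planned.

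The cost is SAP text and one table; the urine, glucose and creatinine data are already collected. The downsides are an interval that may be wide and confounding that 16 subjects cannot remove. Three neighbouring matters are separate points and are not settled here: the printed formula for creatinine-normalised UGE (no ratio of it is proposed), the mismatched group variable in the Appendix 2 code, and the differing sample-size wording.

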8. STATISTICAL ANALYSIS

8.1 General Data Handling Rules and Definitions

All data collected on CRFs will be provided in listings, except data collected only for confirmation of study entry criteria and for study administrative purposes. If any treated subject is found to be without valid documented informed consent, that subject's data will be excluded from the report, except as necessary to document the error.

All statistical analyses will be conducted using SAS version 9.4 or newer.

Except where specified, all continuous variables will be summarized with descriptive statistics (the number of non-missing values, mean, standard deviation, median, minimum and maximum) and all categorical variables will be summarized with frequency counts and percentages, by treatment and hepatic function group. Unless otherwise specified, the mean and median will be displayed to 1 more decimal place than the original data, and standard deviation will be displayed to two more decimal places than the original data. All frequencies will be rounded to 1 decimal place.

Missing data will be maintained as missing unless specified otherwise. For variables where missing data is imputed, the analysis dataset will contain one variable with the imputed value and the original variable with missing maintained as missing.

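### A collected post-dose urine glucose below the limit is treated as uncollected, which usually overstates that interval's group UGE; the effect is small and probably uncommon.

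*SAP*

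**What the plan says.** For post-dose urine, SAP 7.3 states that "values below the reported defined limit that appear after pre-dose for PD data (glucose, UGE, creatinine) will be set to missing". The same sentence covers results that are truly absent, so the two cases are handled identically. For the predose collection, "reported pre-dose values that are below the defined limit will be set to zero". SAP Appendix 1 and Protocol 9.6 give the same pair of rules, and none of the three gives a reason for the difference.

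SAP 8.1 adds that "Missing data will be maintained as missing unless specified otherwise", and its continuous summaries use non-missing values. PD results "by hepatic function group and collection interval will be summarized for the PD Population" (SAP 7.2). For the comparison itself, "Descriptive statistics will be used to describe any differences in these PD parameters between treatment groups". For totals, "The total 24-hour and 48-hour quantity of glucose excreted in urine will be calculated by adding the amounts collected during each post-dose interval". Where zeros occur, geometric means are "based only on the subjects without such zero value data". No substitution rule, count or sensitivity analysis brings a below-limit post-dose result back in.

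**The concern.** UGE for an interval is volume times glucose concentration. Protocol 6.6.2.3 has the volume of every batch recorded. A below-limit result therefore places UGE between zero and the limit times that volume, which is information and not a gap. Under the rule, the value leaves the interval summary because it is low. If the rest of the group is quantifiable, the remaining values describe the better responders.

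PD is part of the primary objective in both documents and is judged only from descriptive summaries of about eight subjects per group. No model is planned that would compensate. The comparison between hepatic function groups shifts only if below-limit results are uneven between the groups.

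**Working it through.** The documents give no figure for this effect, so there is none to reproduce. The dose-response form used in step 5 does agree with Protocol 1.2: 20/(20+3.6) = 0.847 and 20/(20+1.2) = 0.943, against the stated 85% and 94%.

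**Inputs from the documents:** 8 subjects per group (SAP 3.2); UGE formula (SAP 7.3); ED50 3.6 mg in healthy subjects (Protocol 1.2); half-life 7.8 to 9.7 h (Protocol 1).

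**Assumptions, because the documents are silent:** lognormal interval UGE with CV 50 to 120%; a limit of 20 mg/dL; 0.5 to 2 L of urine per 12 h.

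**1. Ceiling.** If the deleted subjects truly excreted nothing, the mean is multiplied by 8/(8−k). That is 8/7 = 1.14 for k = 1 and 8/6 = 1.33 for k = 2.

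**2. Lognormal case.** Set the true mean to 1 and treat the limit as a threshold on the amount. Let s = √ln(1+CV²), p = k/8, z = Φ⁻¹(p) and L = exp(−s²/2 + s·z). The ratios to the true mean are:
- deleted: Φ(s−z)/(1−p)
- scored zero: Φ(s−z)
- scored half the limit: Φ(s−z) + p·L/2

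Example for k = 1, CV 50%: s = 0.472, z = −1.150, Φ(1.623) = 0.948, and 0.948/0.875 = 1.083.

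| k of 8 | CV | L | Deleted | Zero | Half limit |
|---|---|---|---|---|---|
| 1 | 50% | 0.519 | 1.083 | 0.948 | 0.980 |
| 1 | 80% | 0.348 | 1.106 | 0.968 | 0.990 |
| 1 | 120% | 0.216 | 1.122 | 0.982 | 0.995 |
| 2 | 50% | 0.650 | 1.166 | 0.874 | 0.956 |
| 2 | 80% | 0.486 | 1.221 | 0.916 | 0.977 |
| 2 | 120% | 0.339 | 1.263 | 0.947 | 0.990 |

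**3. Grams.** The largest assumed limit amount is 2000 mL × 20 mg/dL / 100 / 1000 = 0.4 g. The true mean is then 0.4/L and the bias is (0.4/L) × (ratio − 1).
- k = 1: means 0.77, 1.15 and 1.85 g; bias +0.06, +0.12 and +0.23 g.
- k = 2: means 0.62, 0.82 and 1.18 g; bias +0.10, +0.18 and +0.31 g.

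The gram effect is larger only if one near-non-responder, at x = 0 to 0.4 g, sits among seven subjects averaging M. The bias is then (M − x)/8: about 0.6 g at an assumed M = 5 g and 2.5 g at M = 20 g.

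**4. Direction.** The limit applies to concentration, so I also let volume vary (lognormal, CV 30 to 70%) and dropped the lowest one or two concentrations in simulated groups of 8. The average overstatement was about 3 to 12% for one and 6 to 25% for two. The group mean fell instead in up to about 9% of groups when volume and concentration were independent, and in up to about 27% at a log-correlation of −0.5. The worst case was concentration CV 50% with volume CV 70%.

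**5. How often.** As a rough projection, take the effect as d/(d+3.6) with d = 20 × 0.5^(t/half-life). Interval UGE is a 12-h total, so the effect is averaged over 36 to 48 h. With half-life 7.8 h, d falls from 0.816 to 0.281 mg. The average is ln[(0.816+3.6)/(0.281+3.6)] / (12 × ln 2/7.8) = 0.121. Half-life 9.7 h counted from an assumed 4-h peak gives 0.272. About 12 to 27% of maximal effect therefore remains. At 12.1%, a below-limit result needs a maximal 12-h UGE under 0.1/0.121 = 0.83 g (0.5 L) to 0.4/0.121 = 3.3 g (2 L). At 27.2% the thresholds are 0.37 and 1.5 g. Applying the ED50 to the amount remaining is itself an approximation.

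**The case against.** The best defence is that the rule is prespecified, identical in three places and similar to the PK convention, under which concentrations below the limit after the peak are set to missing. The 20 mg dose is expected to give 85 to 94% of maximal UGE, so nothing in the documents shows that any post-dose sample will be below the limit. The limit, the volumes and the CVs above are all assumed. There is no hypothesis test, and the 80 to 125% boundaries apply to PK only.

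Most of this stands, and it is why the point is minor. The PK parallel does not rescue the rule. A late plasma value is one point on a curve whose area is still computed for the subject, whereas an interval's UGE is itself the summarised outcome.

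A reader might infer more than the documents support:
- **Overstatement is certain.** It is not. A dilute, large-volume sample just under the limit can hold more glucose than a concentrated, small one above it.
- **The hepatic comparison is biased in a known direction.** The documents do not say which group would have more below-limit results.
- **The reports would hide the low value.** Summary tables would not separate low from uncollected. Listings may, since SAP 8.1 lists CRF data and Protocol 6.6.2.3 records volume and time. The listing layouts are in a separate document.
- **The 24-h or 48-h total is lost.** SAP 7.3 adds the amounts collected and can be read as letting such an interval add nothing. The text does not settle this.
- **The event is easily triggered.** Applying the effect remaining at 48 h (7.2%) to the whole last interval would suggest so, but that is the wrong quantity for a 12-h total.

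**Conclusion.** The point holds and is minor. A stated rule removes collected post-dose results because they are low and usually inflates the interval UGE of the affected group. The relative size is about +8 to +12% for 1 of 8 and +17 to +26% for 2 of 8 under the lognormal assumption. The absolute size is at most about 0.06 to 0.31 g for a 0.4 g limit amount, and more only with a near-non-responder among subjects with substantial excretion. Below-limit results are probably uncommon and most plausible at 36 to 48 h. No test is affected. Confidence is moderate: the rule and the usual direction rest on the text, while the size and frequency rest on assumed inputs.

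**What to change.** Amend SAP 7.3 and SAP Appendix 1, and either amend Protocol 9.6 or record the change in SAP Section 10:

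- Keep a collected and analysed post-dose urine with glucose below the limit in the interval summaries and sums. Score it as zero, as is already done predose, and use half the limit times the measured volume as a sensitivity check.
- Report the number of such values by group and interval. This is needed because zeros still drop out of the geometric means.
- Reserve missing for urine not collected or not analysed. A below-limit creatinine may stay missing, since no ratio can be formed from it.
- State that a below-limit interval contributes its substituted value to the 24-h and 48-h totals and does not make them missing.

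The cost is two or three sentences and one count per interval table, with no new data. The substituted value is an assumption and leaves a smaller bias the other way. From the table above, zero gives about −2 to −5% (1 of 8) or −5 to −13% (2 of 8), and half the limit gives about −0.5 to −2% or −1 to −4%.
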